4.6 VARIABLES

The outcomes of interest are severe complications of diarrhoea including dehydration that requires intravenous rehydration, dehydration that requires oral rehydration with solutions of electrolytes, electrolyte imbalance (potassium and sodium), oliguria, anuria, new onset-thromboembolism, new-onset orthostatic hypotension, new-onset syncope, new-onset dizziness, new-onset vertigo, acute renal failure, hypovolemic shock, hospitalisation due to diarrhoea, stupor, coma, or death.

All variables will be identified using diagnostic and procedure codes from general practitioner (GP) electronic medical records. IBS type and safety outcomes will be validated through a questionnaire to physicians treating the cases and controls included in the study.

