Using the latest available information, the sample size across the three countries is approximately 329,000 patients with IBS-C or potential IBS-C, with an exposure to linaclotide rate ranging from 1% to 4%. If the results of the validation of cases are satisfactory with positive predictive value of SCD algorithms in the UK and Spain $\geq 95\%$, information from the whole cohort will be used to estimate risk of developing SCD across the groups of patients with or without linaclotide exposure, under a cohort study design. If the positive predictive values are $< 95\%$, a case-control analysis will be performed. Assuming the percentage of patients exposed to linaclotide among controls is around 1%, a minimum of 401 case-control pairs would be required to detect an $OR \geq 4$ and 745 possible case-control pairs to detect an $OR \geq 3$ with 80% power, under a matched case-control study design. Within the total IBS-C cohort, it is expected to accrue approximately 11,800 algorithm-identified, potential SCD cases. The final number of case-control pairs to be included in the analyses will depend on the performance of SCD algorithms and case validation results and is expected to be sufficient to detect an $OR \geq 3$ at 80% power, given the number of potential SCD cases identified by the algorithms.

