9.2.1.2 CASE DEFINITION

Among patients with IBS-C, SCD cases will be patients suffering from diarrhoea (as documented by diagnostic codes) and subsequently (between the diarrhoea diagnosis date and 45 days afterwards) any of the following outcomes:

- Dehydration that requires intravenous rehydration
- Dehydration that requires oral rehydration with solutions of electrolytes
- Electrolyte imbalance: potassium (serum potassium levels 3.0–3.5 mEq/L or < 3.0 mEq/L) and sodium (serum sodium levels > 150 mEq/L)
- Oliguria (urine output < 400 mL in 24 h)
- Anuria (urine output < 50 mL in 24 h)

-
- New-onset thromboembolism episodes
 - New-onset orthostatic hypotension
 - New-onset syncope
 - New-onset dizziness
 - New-onset vertigo
 - Acute renal failure
 - Hypovolemic shock
 - Hospitalisation due to diarrhoea
 - Stupor
 - Coma
 - Death (death certificates will be requested to confirm the cause of death)

The case index date is the date of the first diarrhoea episode that is followed by the first recording of any of the previous outcomes from the list above.

Results of laboratory tests will be available as recorded into only two of the proposed data sources: in CPRD they are manually recorded, especially when they are abnormal; they are automatically recorded in the SIDIAP but there is no lab data information from the Swedish NPR.

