9.5 STUDY SIZE

If we assume a combined population in the UK, Sweden, and Spain of approximately 120 million people (Eurostat, 2014), a prevalence of IBS recorded in primary care of 3.5% (Harkness et al., 2013) and roughly one-third of those corresponding to IBS-C (Tillisch et al., 2005), then the three proposed databases could be expected to include around 216,000 active IBS-C patients. By December 2016, it was estimated that approximately 9,665 patients would have been exposed to linaclotide in the three target databases, for a combined exposure of more than 4,572 patient-years, with the UK contributing approximately 28% of patients, Spain 25%, and Sweden 47%. These estimated number of patients exposed to linalcotide is now expected to be reached by end of December 2017, so the data collection period has been extended accordingly.

Linaclotide clinical trial results (12 and 26 weeks in length) suggest that about 3% of IBS-C patients exposed to placebo and 19.6% of IBS-C patients exposed to linaclotide will experience diarrhoea over those periods, predominantly within the first weeks of initiating therapy. Among them, 4% in the placebo group and 10.1% in the linaclotide-exposed group will experience severe diarrhoea. Therefore, severe diarrhoea was experienced by 0.13% of all IBS-C patients exposed to placebo and by 1.99% of IBS-C patients exposed to linaclotide (Chey et al., 2012; Rao et al., 2012). Other treatments for patients with IBS-C are also associated with diarrhoea, usually of mild severity (Wood, 2012). Information sent to healthcare professionals by the manufacturer of a drug sometimes prescribed for IBS-C patients in the United States (US) warned of very serious diarrhoea complicated with hypovolaemia, hypotension, and syncope that required admission to the hospital and intravenous therapy in approximately one in 2,500 patients (or 0.04%) (Wooltorton, 2004).

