Initially, we proposed conducting the study with data collected up to December 2016, but based on the patients counts accrued by December 2016, the data collection period was extended. In the current version of the protocol, the data collection period has been extended to the date of the most recent data available in HES and CPRD at the time of data access for the UK only. As CPRD including Aurum data is about two times larger than the last data extraction, we expect more than 200,000 patients with IBS-C in CPRD. Among them, based on market uptake forecasts, we would also expect having around 2,000 patients exposed to linaclotide by that date (as potential risk factor of interest, or approximately 1% of patients with IBS-C).

If SCD occurs with a frequency of 0.05% among patients with IBS-C (cases) and we select one or more controls per case, then 94 case-controls sets would allow the detection of OR = 4 (or larger), with 80% power for a risk factor present in 5% of controls (approximately the expected proportion of patients with IBS-C exposed to linaclotide).

If we assume that SCD occurs with a frequency of 0.08%, then around 168 case-control sets would allow the detection of OR = 3 or larger, with 80% power for a risk factor present in 5% of controls (in bold in Table 3).

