The CPRD provides a large, diverse, and representative sample of UK people using primary care services, which allows for generalizability of the study findings to the broader UK population. The General Practice Research Database (GPRD), predecessor to CPRD, has been widely used for observational studies, with over 890 studies published to date in peer-reviewed journals. The SIDIAP database includes information for 90% of the population in Catalonia, a region in northeast Spain, and resembling the data collected by the UK databases. One limitation is that date of prescription is only available for the first prescription and, thereafter, only an approximate date of dispensation is available. For Sweden, the NPR and PDR cover the entire Swedish population and have been previously used in observational studies including drug utilisation ones. However, no primary care data will be available, so diagnoses will be those determined by a specialist, which are expected to be required for the variables of interest for this study. The PDR is not complete with regard to drugs used in nursing homes.

According to the National Board of Health and Welfare, about 1% of people aged 65–79 years live in nursing homes, and about 20% of people aged 80 or more years live in nursing homes in Sweden [Socialstyrelsen]. This may be reflected in potential lower numbers of elderly patient using linacotide identified in Sweden.

The validity of research findings based on CPRD data and data from the other databases depends on the quality and completeness of the data recorded. We are only able to identify comorbidities for which the patient has consulted their GP. Referrals are not always uniformly coded and may appear as free-hand text or letters within the database.

Interval censoring might have an impact on the precision of the results.

Additionally, the proposed linked data sources (i.e., HES OP, HES AE and HES APC) have different linkage coverage periods. In particular, HES OP and HES AE linkage periods are considerably shorter than that of HES APC. This might increase the risk of SCD cases being underestimated. Finally, potential SCD are not classified by severity.

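### SCD is modelled as one yes/no outcome mixing mild and serious events, so the linaclotide OR can understate the risk of the serious ones; add a pre-specified serious-SCD analysis

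*Protocol*

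**What the plan says.** Protocol section 9.2.1.2 makes a patient a case when diarrhoea is followed within 45 days by any one item on a list. Section 9.3.2 repeats the list and calls its items primary endpoints. The list includes "New-onset dizziness", "New-onset vertigo" and "Dehydration that requires oral rehydration with solutions of electrolytes". The abstract (section 4.6) shows in one run how far it extends: "new-onset dizziness, new-onset vertigo, acute renal failure, hypovolemic shock, hospitalisation due to diarrhoea, stupor, coma, or death".

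Section 9.7.3.1 enters SCD in the conditional logistic model as a single yes/no variable. Section 9.7.2.2 uses the same endpoint in the Cox model. The closing sentence of section 9.9 reads "Finally, potential SCD are not classified by severity", and no remedy is attached.

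One component is separated: section 9.7.2.1 describes the incidence of death after diarrhoea. That belongs to the cohort analyses, which estimate SCD only if the positive predictive value is at least 95% and the negative predictive value at least 99% (sections 9.7.1 and 9.7.2.2). The sensitivity analyses in section 9.7.3.1 deal with cases and controls that could not be validated, not with severity.

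**The concern.** The study is meant to estimate the risk of severe complications of diarrhoea. An outcome that any one item can trigger gives an OR that averages over the items, and the commonest items dominate the average. If those are the milder, less specific ones, and linaclotide affects them less than it affects admission or renal failure, the pooled OR lies closer to 1 than the OR for the serious events. A modest pooled OR could then be read as reassurance about serious harm that the analysis does not give.

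If validation misses its thresholds, only the case-control analysis of pooled SCD remains. The protocol then plans no separate result for any component, death included.

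**Working it through.** **Inputs from the Protocol.** Two-sided alpha 0.05 and 80% power, 1:1 matched pairs (Table 3). Linaclotide exposure among controls about 1%; 401 pairs for OR 4 and 745 for OR 3; about 11,800 potential cases; a stated aim of detecting OR 3 or more (section 4.8).

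**Inputs assumed, because the Protocol does not give them.** The serious share of cases, s: 10%, 20% or 50%. The linaclotide OR for serious items: 4. The OR for the milder items: 1 as the worst case for dilution, with 2 as an alternative.

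**Step 1: reproduce the plan's figures.** The matched-pair formula is

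n = m / d, with m = (z_α/2 + z_β·√(π(1−π)))² / (π − 0.5)², π = OR/(1+OR), d = p0(1−p1) + p1(1−p0), p1 = OR·p0/(1 + p0(OR−1)).

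Here z_α = 1.960 (so z_α/2 in the formula is 0.980) and z_β = 0.842.

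- OR 4, p0 = 1%: π = 0.8, m = 19.26, p1 = 0.0388, d = 0.0481, n = 400.8, so 401 pairs.
- OR 3, p0 = 1%: π = 0.75, m = 28.92, d = 0.0388, n = 744.9, so 745 pairs.

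Both agree with Table 3.

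**Step 2: the pooled OR.** With controls drawn from the risk set, the OR estimates a rate ratio. The rate of any-component SCD is the sum of the component rates, so

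OR_pooled = s·OR_serious + (1−s)·OR_mild,

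where s is the serious share among unexposed cases.

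| Serious share | Pooled OR, mild OR 1 | Pairs for 80% power, mild OR 1 | Pooled OR, mild OR 2 |
|---|---|---|---|
| 10% | 0.1×4 + 0.9×1 = 1.3 | 20,218 | 0.1×4 + 0.9×2 = 2.2 |
| 20% | 0.2×4 + 0.8×1 = 1.6 | 5,668 | 0.2×4 + 0.8×2 = 2.4 |
| 50% | 0.5×4 + 0.5×1 = 2.5 | 1,181 | 0.5×4 + 0.5×2 = 3.0 |

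If s is instead the share among all cases, the pooled ORs with a mild OR of 1 are 1.29, 1.59 and 2.48, which changes nothing of substance.

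**Step 3: would the pooled effect still be detected?** Solve the same formula for power at 1% exposure with a mild OR of 1. With 20% serious, power is about 82% at 5,900 pairs and 98% at 11,800. With 10% serious it is about 57% at 11,800. Detection therefore depends on how many cases validate and on the serious share. The understatement of the serious OR does not depend on the number of pairs.

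**The case against.** The strongest objection is that the milder items may belong to the harm. Section 7 lists dizziness among the ways that dehydration presented in post-marketing surveillance. A mild OR of 1 is therefore a worst case, not an expectation. If linaclotide raised the milder items as much as the serious ones, there would be no dilution. This stands, and it is why the result is conditional.

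Second, size helps. With several thousand validated pairs the pooled effect may well be detected, as step 3 shows. A reader might infer that the composite would hide a serious effect altogether. The documents do not support that: it would need a small serious share or few validated cases, and neither figure is given.

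Third, a reader might set the expected case yield ("it is expected to accrue approximately 11,800 algorithm-identified, potential SCD cases", which is 11,800/329,000 = 3.6%) against the 0.05% and 0.08% in section 9.5.2 and conclude that most cases are mild. That does not follow. The two low figures are conditional scenarios, Table 2 runs up to 1.0%, and the yield is before validation, so the excess may be false positives. Nor does the account in section 9.5 of "very serious diarrhoea complicated with hypovolaemia, hypotension, and syncope that required admission to the hospital" define the harm expected here, because it concerns another drug.

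Fourth, UK validation filters severity to some extent. Question 8 of the GP questionnaire lets the physician skip the complications list when the episode needed nothing beyond diet, oral rehydration or stopping treatment. The filter is incomplete: question 9 still offers oral electrolyte rehydration, Spain uses free-text review, and Sweden has no validation.

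Last, a separate SAP is listed in Annex 1 and might add component analyses. The point does not rest on that silence. The Protocol itself fixes a single outcome and records the lack of severity classification as a limitation. Disclosing a limitation does not supply an analysis.

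**Conclusion.** The point holds in conditional form. The Protocol pools mild and serious events in one modelled outcome, does not classify by severity, and separates only death, as an incidence that depends on validation. If linaclotide acts less strongly on the milder items, the pooled OR understates the serious-event OR. With a serious OR of 4, a mild OR of 1 and 10% to 50% of cases serious, it is about 1.3 to 2.5, below the target of 3. With a mild OR of 2 it is 2.2 to 3.0. The serious share and both component ORs are assumptions. The composite remains a legitimate main outcome; what is missing is a planned result that speaks to the serious events. This is a worthwhile, cheap improvement rather than a flaw that invalidates the study.

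**What to change.** Keep the composite, the matching and the model. In section 9.7.3.1, whatever the validation result, and in section 9.7.2.2 if the cohort analysis is run, pre-specify before results are seen:

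- case counts by triggering component, by country;
- the same linaclotide model on a named serious-SCD subset, reported beside the all-SCD estimate.

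The sponsor's clinical team should define the subset in advance, from components that have their own codes or flags. Examples are hospitalisation due to diarrhoea, acute renal failure, hypovolaemic shock and death. Whether syncope, hypotension or others belong is for that team to decide. Intravenous rehydration should be used only where procedure or validation data identify it, because the dehydration codes in Annex 3 (Tables 14 to 16) do not separate it from oral rehydration. Amend the last sentence of section 9.9 to refer to this analysis.

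The cost is an outcome definition and a repeat of the same model on existing matched sets. The subset will have fewer cases and a wider interval, and there will be one more secondary result to interpret. UK hospitalisation will be under-captured after HES linkage ends: Table 1 gives 31 March 2021 for admitted patient care, against October and November 2023 for CPRD. The report should say so.

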9.10 OTHER ASPECTS

No further aspects to be considered.

10 PROTECTION OF HUMAN SUBJECTS

Institutional review board approval and/or any other required reviews of the study protocol by specific committees will be obtained in accordance with applicable national and local regulations.

The study will be conducted in accordance with the International Society for Pharmacoepidemiology's (ISPE) *Guidelines for Good Pharmacoepidemiology Practices (GPP)* (2007), the European Network of Centres for Pharmacoepidemiology and Pharmacovigilance's (ENCePP) *Guide on Methodological Standards in Pharmacoepidemiology* (ENCePP, 2011a). The ENCePP *Checklist for Study Protocols* (ENCePP, 2011b) will be completed.

The study will be registered in the ENCePP *Electronic Register of Studies* (ENCePP, 2010) after regulatory endorsement of the protocol.

The study will comply with the definition of the non-interventional (observational) study provided in Article 2(c) of Directive 2001/20/European Commission and its refinement provided in Chapter I.7 Section 1 of *Volume 9A of the Rules Governing Medicinal Products in the EU: Guidelines on Pharmacovigilance for Medicinal Products for Human Use* (European Commission, 2008), and referred to in the International Conference on Harmonisation (ICH) of Technical Requirements for Registration of Pharmaceuticals for Human Use's *Pharmacovigilance Planning* (ICH, 2004) and the *Guideline on Good Pharmacovigilance Practices, Module VIII—Post-Authorisation Safety Studies* (European Medicines Agency [EMA], 2012a).

11 MANAGEMENT AND REPORTING OF ADVERSE EVENTS (AE)/ADVERSE REACTIONS

For studies in which the research team uses only data from automated healthcare databases, the ISPE provides the following guidance:

'Aggregate analysis of database studies can identify an unexpected increase in risk associated with a particular exposure. Such studies may be reportable as study reports, but typically do not require reporting of individual cases. Moreover, access to automated databases does not confer a special obligation to assess and/or report any individual events contained in the databases. Formal studies conducted using these databases should adhere to these guidelines.' (ISPE, 2007, Section VI)

The EMA *Guideline on Good Pharmacovigilance Practices, Module VI*, provides the following guidance:

'For non-interventional study designs which are based on secondary use of data, such as studies based on medical chart reviews or electronic healthcare records, systematic reviews or meta-analyses, adverse reactions reporting is not required. Reports of adverse events/reactions should only be summarised in the study report, where applicable.'
(EMA, 2012b, Section C.1.2.1)

The linaclotide PASS does not require adverse events (AEs) to be reported in an expedited manner to European authorities. Identified AEs/reactions will be summarised in the final study report.

AEs that are communicated in response to the physician questionnaires will be reported according to the *European Good Pharmacovigilance Practices, Module VI* (EMA, 2012b). Procedures for the collection and reporting to AbbVie of AEs/reactions identified during the study conduct will be agreed upon with AbbVie and put in place in accordance with the provisions of *Module VI, Management and Reporting of Adverse Reactions to Medicinal Products*, from the EMA.

12 PLANS FOR DISSEMINATING AND COMMUNICATING STUDY RESULTS

12.1 REGULATORY COMMUNICATION PLAN

The study protocol, study status, and report(s) will be included in regulatory communications in line with the RMP, PSUR, and other regulatory milestones and requirements.

12.2 PUBLICATION AND COMMUNICATION PLAN

Any publication resulting from the work outlined in this proposal will be discussed with AbbVie. Evidera will ensure AbbVie has adequate time to review and comment on any manuscript or abstract developed. For all publications of Evidera project work, Evidera adheres to the authorship definitions and requirements as stated in the *Uniform Requirements for Manuscripts Submitted to Biomedical Journals* from the International Committee of Medical Journal Editors (ICMJE) 2013, repeated in part, as follows:

- Authorship credit should be based on: 1) substantial contributions to conception and design, or acquisition of data, or analysis and interpretation of data; 2) drafting the article or revising it critically for important intellectual content; and 3) final approval of the version to be published. Authors should meet conditions 1, 2 and 3.
- All persons designated as authors should qualify for authorship and all those who qualify should be listed
- Each author should have participated sufficiently in the work to take public responsibility for appropriate portions of the content
- Acquisition of funding, collection of data, or general supervision of the research group, alone, does not justify authorship

Study results will be published following guidelines of the ICMJE (2010) and communication in appropriate scientific venues (e.g., ISPE) will be considered. When reporting results of this study, the appropriate Strengthening the Reporting of Observational Studies in Epidemiology (STROBE) checklist will be followed (STROBE, 2007).

In its *Guidelines for Good Pharmacoepidemiology Practices*, ISPE contends that *'there is an ethical obligation to disseminate findings of potential scientific or public health importance'* (ISPE, 2007, Section V). This would include results pertaining to the safety of a marketed medication. Study results will be published following guidelines, including those for authorship, established by the ICMJE (2010).

The marketing authorisation holder and the investigator have agreed on a publication policy allowing the principal investigator to prepare publications independently based on the study results, irrespective of data ownership. The marketing authorisation holder will be entitled to view the results and

interpretations included in the manuscript, and provide comments prior to submission of the manuscript for publication (EMA, 2012a, Section VIII.B.7).

ANNEX 1. LIST OF STAND-ALONE DOCUMENTS

Number	Document reference number	Date	Title
1	SAP version identifier: 2.1	07/06/2016	Linaclotide Safety Study for the Assessment of Diarrhoea—Complications and Associated Risk Factors in Selected European Populations with IB-C Statistical Analyses Plan

ANNEX 2. ENCEPP CHECKLIST FOR STUDY PROTOCOLS

Study title:

Linacotide Safety Study for the Assessment of Diarrhoea Complications and Associated Risk Factors in Selected European Populations with IB C

Study reference number:

EUPAS15353

Section 1: Milestones	Yes	No	N/A	Section Number
